8.2.1.3. Potentially Clinically Significant Laboratory Abnormalities

Abnormal laboratory values (excluding Hgb, reticulocytes, haptoglobin, bilirubin, and LDH) will also be evaluated by determining the number and percentage of subjects with at least one potentially clinically significant laboratory abnormality over the course of the study that also represents a worsening from baseline. The potentially clinically significant levels are based on Grade 2 or higher thresholds from the CTCAE v4.03 where possible, or are defined by Sponsor's safety group. Subjects who have a post baseline laboratory value that meets the criteria for being potentially clinically significant but do not have a baseline value will be included in the numerator for determining the percentage of subjects with an abnormality. Data collected from unscheduled visits will be included in this analysis.

8.2.2. SLE Panel and Serum Disease-related Biomarkers

SLE panel (below) and serum disease-related biomarkers (below) at baseline and post baseline visits, along with change from baseline, will be summarized with descriptive statistics for the Safety Analysis Set. Additional exploratory analyses may be performed to examine the relationship between biomarkers and efficacy or safety parameters.

Systemic Lupus Erythematosus Panel

Antinuclear antibody (ANA), multiplex with dsDNA, Anti-La/SSB antibody (SS-B), Anti-ribonucleoprotein antibody (RNP), Anti-Smith antibody (Sm), Anti-Ro/SSA antibody (SS A), Anti-scleroderma antibody (Scl-70), Anti-Chromatin antibody, Anti-Jo-1 antibody, Anti-Centromere B antibody, Circulating immune complexes (CIC).

Disease-Related Biomarkers

DAT (polyspecific, anti-IgG & anti-C3d), LDH isoforms, cold agglutinin (CAg) titre, IgG subsets (IgA, IgD, IgG, IgM), CAg thermal amplitude. Vaccine titers, if collected, will be presented in a listing only.

8.2.3. Anti-drug Antibody (ADA)

Subjects who discontinue treatment early in Part A will be evaluated for anti-drug antibodies. Subjects with negative and positive anti-drug antibodies will be listed along with the associated titer if available.

8.3. ECG and Vital Signs

8.3.1. Electrocardiograms (ECG)

The proportion of subjects with clinically significant change from baseline in ECG findings will be summarized by visit.

8.3.2. Vital Signs

Vital signs (systolic and diastolic blood pressure, pulse, respiratory rate, and temperature) will be summarized for the observed values and change from baseline using descriptive statistics for the Safety Analysis Set.

The number and percentage of subjects with potentially clinically relevant post-baseline abnormalities will be presented. The criteria for potentially clinically relevant post-baseline abnormalities are shown below in [Table 9](#).

Table 9: Criteria to Determine Potentially Clinically Relevant Abnormalities in Vital Signs

Vital Sign	Criteria for Abnormalities
Temperature	> 38°C and an increase from pre-dosing of at least 1°C
Pulse	> 120 beats per minute post-baseline or an increase from pre-dosing of more than 20 beats per minute; < 50 beats per minute post-baseline or a decrease from pre-dosing of more than 20 beats per minute
Systolic Blood Pressure	> 180 mmHg post-baseline or an increase from pre-dosing of more than 40 mmHg; < 90 mmHg post-baseline or a decrease from pre-dosing of more than 30 mmHg
Diastolic Blood Pressure	> 105 mmHg post-baseline or an increase from pre-dosing of more than 30 mmHg; < 50 mmHg post-baseline, or a decrease from pre-dosing of more than 20 mmHg
Respiratory Rate	> 35 breaths per minute post-baseline; < 10 breaths per minute post-baseline

9. PHARMACOKINETIC AND PHARMACODYNAMIC ANALYSIS

9.1. Pharmacokinetic Analysis

Plasma BIVV009 concentrations will be listed by subject, nominal visit, date and time of collection and study day. Summary statistics of plasma BIVV009 concentrations will be presented by nominal visit and study day including n, mean, standard deviation, coefficient of variation, geometric mean, median and range. Individual and mean plasma BIVV009 concentration-versus-time profiles will be plotted.

9.2. Pharmacodynamic Analysis

Descriptive statistics including number of observations, mean, SD, median, minimum, and maximum will be presented for continuous parameters. Categorical variables will be presented with the number and percentage in each category. Summary descriptive statistics (absolute values and changes from baseline) and individual subject listings will be presented for all PD parameters by time point and study day.

10. CHANGES FROM PREVIOUS VERSION

The following changes have been made to Version 1.0 of the SAP:

- Calculation of exposure have been clarified.
- Components for the primary endpoint (receiving transfusion and prohibited medication from Week 5 to Week 26) have been clarified.
- Analysis of rate of change in hemoglobin has been removed.
- Summaries and analyses of solicited symptomatic anemia have been clarified.
- Summaries of FACIT-Fatigue individual item responses have been removed as they will be provided in a separate FACIT-Fatigue analysis plan.
- Summaries of SF-12 have been clarified.

12. LIST OF TABLES AND FIGURES

List of tables and figures

Background/Demography
Part A: Summary of disposition
Part A: Summary of enrollment by country and site
Part A: Summary of subjects attending each visit
Part A: Summary of demographics and baseline characteristics
Part A: Summary of all major protocol deviations
Part A: Summary of important protocol deviations impacting efficacy
Part A: Summary of medical history
Part A: Summary of thromboembolic medical history
Part A: Summary of targeted medical history
Part A: Summary of prior bone marrow biopsy review
Part A: Summary of Gilbert's syndrome testing at screening
Part A: Summary of selected disease-related biomarkers at screening
Part A: Summary of CAD related anemia symptoms prior to first dose
Part A: Summary of other CAD related disease characteristics prior to first dose
Part A: Summary of hemolytic laboratory parameters prior to first dose
Part A: Summary of transfusion history
Part A: Summary of transfusions during screening period
Part A: Summary of immunization review /vaccination
Part A: Summary of targeted prior therapy
Part A: Summary of prior CAD medications
Part A: Summary of concomitant medication
Part A: Summary of concomitant CAD medications
Part A: Summary of protocol-prohibited concomitant CAD medications
Part A: Summary of concomitant non-drug treatments
Exposure/Dosing
Part A: Summary of BIVV009 exposure
Part A: Summary of BIVV009 administration by visit and overall compliance
Efficacy: Primary
Part A: Summary of primary endpoint: components of treatment response
Part A: Summary of primary endpoint: treatment response - Composite estimand
Part A: Summary of primary endpoint: components of treatment response based on hemoglobin \geq lower limit of normal- sensitivity analysis
Part A: Summary of primary endpoint: treatment response based on hemoglobin \geq lower limit of normal
Part A: Summary of primary endpoint: treatment response - Completer estimand - sensitivity analysis
Part A: Summary of primary endpoint: treatment response - Per-protocol estimand - sensitivity analysis
Part A: Summary of treatment response by subgroup - Composite estimand
Part A: Forest plot of treatment response and 95% CI by subgroups – Composite estimand
Efficacy: Secondary
Part A: Summary of change from baseline in hemoglobin (g/dL) at treatment assessment timepoint - Hypothetical estimand - MMRM
Part A: Summary of change from baseline in hemoglobin (g/dL) at treatment assessment timepoint - De-facto estimand - MMRM
Part A: Summary of change from baseline in hemoglobin (g/dL) at treatment assessment timepoint - Hypothetical estimand – MI

[figure not shown]
Part A: Summary of change from baseline in bilirubin (umol/L) at treatment assessment timepoint (excluding subjects with Gilbert's syndrome) - Hypothetical estimand - MMRM
Part A: Summary of change from baseline in bilirubin (umol/L) at treatment assessment timepoint (excluding subjects with Gilbert's syndrome) - De-facto estimand - MMRM
Part A: Summary of change from baseline in bilirubin (umol/L) at treatment assessment timepoint (excluding subjects with Gilbert's syndrome) - Hypothetical estimand - MI
Part A: Summary of change from baseline in lactate dehydrogenase (U/L) at treatment assessment timepoint - Hypothetical estimand - MMRM
Part A: Summary of change from baseline in lactate dehydrogenase (U/L) at treatment assessment timepoint - De-facto estimand - MMRM
Part A: Summary of change from baseline in lactate dehydrogenase (U/L) at treatment assessment timepoint - Hypothetical estimand - MI
Part A: Summary of change from baseline in FACIT-Fatigue score at treatment assessment timepoint - Hypothetical estimand - MMRM
Part A: Summary of change from baseline in FACIT-Fatigue score at treatment assessment timepoint - De-facto estimand - MMRM
Part A: Summary of change from baseline in FACIT-Fatigue score at treatment assessment timepoint - Hypothetical estimand - MI
Part A: Summary of number of transfusions and units after the first 5 weeks of study drug administration
Efficacy: Exploratory - Hemolytic Parameters
Part A: Summary of change from baseline in hemoglobin (g/dL) by visit - Observed
Part A: Summary of change from baseline in bilirubin (umol/L) by visit - Observed
Part A: Summary of change from baseline in lactate dehydrogenase (U/L) by visit - Observed
Part A: Summary of change from baseline in haptoglobin (g/L) by visit - Observed
Part A: Summary of change from baseline in absolute reticulocyte ($10^9/L$) by visit - Observed
Part A: Plot of mean hemoglobin (g/dL) (+/- SE) by visit - Observed
Part A: Plot of mean change from baseline in hemoglobin (g/dL) (+/- SE) by visit - Observed
Part A: Plot of mean bilirubin (umol/L) (+/- SE) by visit (excluding subjects with Gilbert's syndrome) - Observed
Part A: Plot of mean change from baseline in bilirubin (umol/L) (+/- SE) by visit (excluding subjects with Gilbert's syndrome) - Observed
Part A: Plot of mean lactate dehydrogenase (U/L) (+/- SE) by visit - Observed
Part A: Plot of mean change from baseline in lactate dehydrogenase (U/L) (+/- SE) by visit - Observed
Part A: Plot of mean haptoglobin (g/L) (+/- SE) by visit - Observed
Part A: Plot of mean change from baseline in haptoglobin (g/L) (+/- SE) by visit - Observed
Part A: Plot of mean absolute reticulocyte ($10^9/L$) (+/- SE) by visit - Observed
Part A: Plot of mean change from baseline in absolute reticulocyte ($10^9/L$) (+/- SE) by visit - Observed
Part A: Summary of proportion of subjects normalizing hemolytic parameters at the treatment assessment timepoint - Observed
Part A: Summary of time to first normalization of hemolytic parameters (1) - Observed
Part A: Summary of time to first normalization of hemolytic parameters (2) - Observed
Part A: Plot of hemoglobin (g/dL) by visit by response - Observed
Part A: Summary of shift to non-detectable/detectable in haptoglobin by visit - Observed
Efficacy: Exploratory - CAD Events
Part A: Summary of incidence of solicited symptomatic anemia by visit
Part A: Summary of incidence of solicited symptomatic anemia improvement by visit
Part A: Summary of incidence of other CAD-related symptoms by visit

[figure not shown]
Part A: Summary of incidence of thromboembolic events after the first 5 weeks of BIVV009 administration
Part A: Summary of time to first transfusion after the first 5 weeks of BIVV009 administration
Part A: Plot of time to first transfusion after the first 5 weeks of BIVV009 administration
Part A: Summary of time to first transfusion including the first 5 weeks of BIVV009 administration
Part A: Summary of transfusions by study period
Efficacy: Exploratory - PRO
Part A: Summary of FACIT-Fatigue score and change from baseline by visit
Part A: Plot of mean FACIT-Fatigue score (+/- SE) by visit
Part A: Summary of EQ-5D index score and change from baseline by visit
Part A: Summary of EQ-5D-5L visual analogue scale (VAS) and change from baseline by visit
Part A: Summary of EQ-5D-5L descriptive system
Part A: Summary of SF-12 component scores and change from baseline by visit
Part A: Summary of SF-12 sub-scale scores and change from baseline by visit
Part A: Summary of Patient's Global Impression of Change (PGIC)
Part A: Summary of Patient's Global Impression of Fatigue Severity (PGIS) by visit
Part A: Summary of Patient's Global Impression of Fatigue Severity (PGIS) change from baseline by visit
Safety: Adverse Events
Part A: Overall summary of treatment-emergent adverse events
Part A: Summary of treatment-emergent adverse events
Part A: Summary of treatment-emergent adverse events by preferred term in descending order of incidence
Part A: Summary of Grade 3 or higher TEAEs by preferred term in descending order of incidence
Part A: Summary of treatment-emergent adverse events by severity
Part A: Summary of treatment-emergent adverse events by relationship to treatment
Part A: Summary of treatment-emergent serious adverse events
Part A: Summary of treatment-emergent serious adverse events by preferred term in descending order of incidence
Part A: Summary of related treatment-emergent serious adverse events
Part A: Summary of treatment-emergent adverse events within 24 hours of the start of infusion
Part A: Summary of infections of Grade 3 or higher by preferred term
Part A: Incidence of hemolytic breakthrough
Safety: Laboratory
Part A: Summary of hematology values and change from baseline by visit
Part A: Summary of chemistry values and change from baseline by visit
Part A: Summary of coagulation panel by visit
Part A: Shifts from baseline to minimum/maximum post-baseline value for laboratory results: Hematology
Part A: Shifts from baseline to minimum/maximum post-baseline value for laboratory results: Chemistry
Part A: Summary of shift to low (high) for laboratory results: Hematology
Part A: Summary of shift to low (high) for laboratory results: Chemistry
Part A: Summary of potentially clinically significant laboratory abnormalities: Hematology
Part A: Summary of potentially clinically significant laboratory abnormalities: Chemistry
Part A: Summary of systemic lupus erythematosus (SLE) based on combined SLE panel parameters
Part A: Summary of systemic lupus erythematosus (SLE) by each SLE panel parameter
Part A: Summary of laboratory results and change from baseline by visit: Disease-Related Biomarkers (1)

Part A: Summary of laboratory results by visit: Disease-Related Biomarkers (2)
Part A: Summary of ECG clinical interpretations by visit
Part A: Summary of ECG clinical interpretation shifts from baseline
Part A: Summary of vital signs values and change from baseline
Part A: Summary of potentially clinically significant vital signs
PK/PD
Part A: Summary of BIVV009 plasma concentrations by visit
Part A: Plot of BIVV009 concentrations over time by subject
Part A: Plot of mean (+/- SE) BIVV009 concentration over time
Part A: Summary of PD parameter results and change from baseline by visit

[figure not shown]
13. APPENDICES

[figure not shown]
Appendix A: Scoring Algorithm for FACIT-F

[figure not shown]

[figure not shown]
Appendix B: EQ-5D-5L Questionnaire Score Definitions

[figure not shown]

[figure not shown]
Appendix C: 12-item Short Form Survey (SF-12)

[figure not shown]

1. INTRODUCTION

BIVV009-03 is an open-label, single-arm, multicenter study in patients with primary cold agglutinin disease (CAD) who have hemoglobin (Hgb) level ≤ 10 g/dL and a recent history of blood transfusion. Eligible patients received study drug and underwent safety and efficacy assessments for 6 months (26 weeks) in Part A of the study.

Following completion of the initial 6-month treatment period, patients will roll into the long-term safety study (Part B) where they will continue to receive the study drug, BIVV009. Part B will run for 1 year following last patient out (LPO) under Part A. As in Part A, patients will be dosed with BIVV009 every 2 weeks. On-site visits will be completed approximately every 3 months (at a minimum) for collection of pharmacokinetics (PK) and pharmacodynamics (PD) samples and for additional safety and efficacy measures. The study will be complete 12 months following LPO for Part A at which time all patients receiving on-going treatment will proceed to an End-of-Study (EOS) visit 9 weeks after the last administration of study drug.

This statistical analysis plan contains information pertaining to definitions of analysis sets and derived variables, and statistical methods for the analysis of efficacy, safety, PK, and PD for Part B of the referenced study.

2. STUDY OBJECTIVES AND ENDPOINTS

2.1. Study Objectives

2.1.1. Primary Objective

The primary objective of Part B is to evaluate the long-term safety and tolerability of BIVV009 in patients with CAD.

2.1.2. Secondary Objective

The secondary objective of Part B is to investigate the durability of response during long-term treatment with BIVV009 in patients with CAD.

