A patient will be considered a responder in Part A if he or she did not receive a blood transfusion from Week 5 through Week 26 (EOT) and did not receive treatment for CAgD beyond what is permitted per protocol. Additionally, the patient's Hgb level must meet either of the following criteria:

- Hgb level is ≥ 12 g/dL at the treatment assessment endpoint (defined as mean value from Weeks 23, 25, and 26), *or*
- Hgb increased ≥ 2 g/dL from baseline (defined as the last Hgb value before administration of the first dose of study drug) at treatment assessment endpoint

Note: Any patient withdrawing from the study after Week 5 and prior to the Week 23 visit will be considered a non-responder.

A list of excluded concomitant medications, as well as allowed concomitant medications with restrictions, is provided in [Section 6.2.6](#). Beyond the permitted concomitant medications, study drug, and transfusions, patients may receive no other therapies for the treatment of CAgD while enrolled in this study; patients requiring other treatment for their CAgD in Part A will be withdrawn from the study and counted as non-responders. These patients will not be eligible to participate in Part B.

Part B

Following completion of dosing in the 6-month treatment period, patients will continue to receive BIVV009 dosing during Part B, the long-term safety and durability of response extension phase. Part B will run for 2 years following last patient out (LPO) under Part A. Patients requiring treatment with permitted concomitant medications and/or transfusions will not be discontinued from the study. Patients in Part B will be transfused per the Transfusion Criteria in [Table 1](#). Patients who receive a transfusion during Part B will not be withdrawn from the study.

Patients will be dosed with BIVV009 every 2 weeks, as in Part A. Should patients deviate from their scheduled dosing, a repeat loading dose may be required. On-site visits will be completed ~ every 3 months (at a minimum) for collection of PK, PD and ADA samples during the 1st year of treatment in Part B, then every 6 months and for additional safety and efficacy measures.

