4.3.4 Efficacy endpoints (Part B)

- Hemoglobin
- Bilirubin (total)
- QOL assessments (FACIT-Fatigue, EQ-5D-5L, SF-12, PGIS, and PGIC)
- LDH
- Transfusion requirements
- Haptoglobin

- Total healthcare resource utilization at EOT
- Satisfaction with home infusion

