2.2.2. Efficacy Endpoints

The efficacy endpoints are the following parameters of disease activity:

- Hemoglobin
- Bilirubin (total)
- Lactate dehydrogenase (LDH)
- Haptoglobin
- Reticulocyte Count

- Transfusion requirements
- Incidence of solicited symptomatic anemia
- Incidence of thromboembolic events
- Incidence of hemolytic breakthrough
- Healthcare resource utilization parameters
- QOL assessments (FACIT-Fatigue, EQ-5D-5L, SF-12, PGIS, and PGIC)

Details of the analysis of efficacy endpoints are described in [Section 7](#).

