3.1.1. Study Sample

Patients in Part B will be a subset of the patients enrolled in Part A. All patients who complete Part A, including those receiving transfusions, will be eligible for Part B. Patients who withdraw from the study in Part A, including those who received prohibited concomitant medications, will not be eligible to participate in Part B. Subject inclusion and exclusion criteria for Part A can be found in Sections 5.1 and 5.2 of the protocol.

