5.1.3. Handling of Missing Data

Best efforts will be utilized to minimize missing values. If a subject discontinues study treatment early, the subject will be asked to complete study assessments at ET/safety follow up visit.

For the analysis of both continuous and categorical data, summary statistics will be computed based on observed data. Since the duration of treatment period varies in Part B, efficacy endpoints by visit will be summarized through 12 months during Part B. Additional summaries beyond 12 months may be computed depending on the enrollment pattern, i.e., the number of subjects attending visits after the Week 77 visit. AE endpoints by visit will be summarized through LPLV in Part B.

For a QOL endpoint, in the event of missing data, the total score will be estimated according to the provision for missing domains in the calculation algorithm of the score. For example, if a subject has missing data in FACIT-F questionnaire at a visit, the prorated FACIT-F score will be calculated if more than 50% of the items (a minimum of 7 out of 13 items) are available. Otherwise, the score is missing.

For the analysis of AEs and concomitant medications/procedures, if the start/stop date of an AE/concomitant medication/procedure is missing or partial, the corresponding study day will be left blank. However, inferences will be made from the partial and missing dates to classify medications as prior and/or concomitant and AEs as treatment emergent or not treatment emergent. These inferences are described in [Section 8.1](#).

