7.3.1. Continuous Endpoints

The continuous endpoints include:

- Hemoglobin
- Bilirubin (total)

The above endpoints will be summarized by visit, starting at Baseline/Day 0 and will continue through the Week 77 visit. Summary tables will include change from baseline and individual summary statistics will follow those presented in [Section 5.2.1](#). For patients with more than 12 months of follow-up in Part B, all endpoints at the Week 79 visit and beyond will be provided in a data listing.

Line plots of mean hemoglobin and bilirubin over time, starting at Baseline/Day 0, will be presented. Additionally, a line plot of mean change from baseline in hemoglobin over time, starting at Baseline/Day 0, will be presented.

Additionally, the following continuous endpoints will be summarized by Study Period using FAS as specified in [Section 5.2.1](#):

- Number of transfusions and total transfusion units
- Annualized number of transfusions and annualized transfusion units

For number of transfusions and total transfusion units, data up to Week 77 will be considered, for both Part B and Combined Study Period summaries. All data after Week 77 will be provided in the listing.

For annualized number of transfusions and annualized transfusion units, all Part B data will be considered. Annualized values will be calculated for each patient using the following formula:

$$\text{Annualized value} = \frac{\text{Number of events during the Study Period}}{\text{Total number of days during the Study Period}} \times 365.25$$

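### Part B's secondary objective is durability of response, but no planned output applies the response criteria after Week 26 or is restricted to Part A responders

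*SAP*

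**What the plan says.** Part B SAP 2.1.2 gives one secondary objective, matching Protocol 3.4: "The secondary objective of Part B is to investigate the durability of response during long-term treatment with BIVV009 in patients with CAD".

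The only definition of response is in Protocol 4.1, Table 2, and it is tied to Part A: "A patient will be considered a responder in Part A if he or she did not receive a blood transfusion from Week 5", a period that ends at the Week 26 visit. It also requires no CAD therapy beyond what the protocol permits, and a mean Hgb over Weeks 23, 25 and 26 that is at least 12 g/dL or at least 2 g/dL above baseline.

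The Part B endpoints are a list of parameters. Part B SAP 2.2.2 introduces them with "The efficacy endpoints are the following parameters of disease activity", and Protocol 4.3.4 has a similar list that includes "Transfusion requirements". Neither list contains maintained response, loss of response or duration of response.

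On who is analyzed and how:
- Entry to Part B (Part B SAP 3.1.1): "All patients who complete Part A, including those receiving transfusions, will be eligible for Part B". The analysis set (4.1) is everyone dosed in Part B.
- Data handling (5.1.3): "For the analysis of both continuous and categorical data, summary statistics will be computed based on observed data".
- Hgb and bilirubin (7.3.1): "The above endpoints will be summarized by visit, starting at Baseline/Day 0 and will continue through the Week 77 visit". Later visits are listed.

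**The concern.** A durability objective asks how many patients who had responded still respond, and for how long. Answering it needs a starting group (the Part A responders), a rule for when response is lost, and a count or time based on that rule. The Part B plan supplies none of these for the composite.

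The nearest general output is the by-visit Hgb mean. It pools Part A responders with non-responders, includes Hgb values supported by transfusion, and is taken over patients still attending. If the plan is followed as written, the stated objective gets no direct estimate. A reader of the report would have to assemble durability from several tables and the listings.

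**Working it through.** **1. The plan's own figures.** Part B has no sample-size or power figure (Part B SAP 3.3). The only design figure is for Part A (Protocol 7.10): 20 patients, a true rate of 66% against 30%, 90% power and a minimum of 11/20. It reproduces: exact binomial power is 89.7%, and the Clopper-Pearson lower bound is 31.5% for 11/20 and 27.2% for 10/20. The point does not depend on this; I use it only for the expected number of responders, 0.66 × 20 = 13.2, about 13.

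**2. What each planned output can detect.**

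| Component of response | Part B output | What it misses |
|---|---|---|
| No transfusion | Kaplan-Meier time to first transfusion (7.3.2); counts and annualized rates (7.3.1) | Whole analysis set, not responders; patients without the event are censored at last assessment (5.2.3), so stopping is not an event |
| No prohibited CAD therapy | Summary table (6.4.1) | Not linked to response |
| Hgb ≥12 g/dL or ≥2 g/dL above baseline | By-visit means (7.3.1); hemolytic breakthrough (7.2.2) | No patient-level count of who still meets the criterion |

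**3. The uncovered path.** Breakthrough needs a fall of at least 2 g/dL since the last scheduled visit, with a worsening hemolysis marker (5.1.1). The transfusion criteria need Hgb below 9 g/dL with symptoms or below 7 g/dL without (3.1.2). Take a responder with baseline 8.5 g/dL who declines from 12 to 9.2 g/dL in seven steps of 0.4 g/dL (7 × 0.4 = 2.8):
- Each step is below 2 g/dL, so there is no breakthrough.
- 9.2 is not below 9, so the transfusion criteria are not met.
- 9.2 < 12 and 9.2 − 8.5 = 0.7 < 2, so neither Table 2 criterion holds.

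This patient has lost the Hgb response, and no summary table records it. The example depends on two conditions: the fall must be gradual, and baseline must be above 9.2 − 2 = 7.2 g/dL.

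**4. Contrast with Part A.** The Part A SAP reports by-visit proportions with Hgb ≥12 g/dL and with a 2 g/dL increase (7.4.1.2). It removes post-transfusion laboratory values under the hypothetical estimand (5.1.4) and lists a plot of Hgb by visit by response (section 12). Part B has no counterpart to these. Its 7-day transfusion rule applies only to the baseline value (Part B SAP 5.1.1).

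**5. How far the mean is diluted (assumed values, not in the documents).** Twenty patients enter Part B: 13 responders with mean change +3.0 g/dL and 7 non-responders with +1.0 g/dL. Starting mean = (13 × 3.0 + 7 × 1.0)/20 = 2.30. Four responders lose response and fall to +0.5:
- Untransfused: (9 × 3.0 + 4 × 0.5 + 7 × 1.0)/20 = 1.80, a fall of 0.50.
- Transfusion adds 1 g/dL: (27 + 4 × 1.5 + 7)/20 = 2.00, a fall of 0.30.
- Transfusion adds 2 g/dL: (27 + 4 × 2.5 + 7)/20 = 2.20, a fall of 0.10.
- All four leave: (27 + 7)/16 = 2.125, a fall of 0.175.

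Maintained response is 9/13 = 69.2% (exact 95% CI 38.6% to 90.9%) in every case. If the patients stay in the study, two losses lower the mean by 0.05 to 0.25 with 11/13 = 84.6% maintained, and six losses lower it by 0.15 to 0.75 with 7/13 = 53.8% maintained. The same loss of response gives quite different mean changes, depending on transfusion and dropout.

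**The case against.** A reader might infer that loss of response is hidden in Part B. The documents do not support that. The Part B SAP plans time to first transfusion with a plot, transfusion counts and annualized rates, and hemolytic breakthrough on all Part B data. It also plans hemolysis markers and symptomatic anemia by visit, prohibited CAD therapy, disposition with reasons for stopping, and listings of all efficacy data. Patients who lose response through transfusion or by leaving would appear in those tables. The mean also moves when response is lost, as the illustration shows.

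Nor does starting the transfusion curve at Week 5 of Part A distort it for responders. By definition they have no transfusion from Week 5 to Week 26, so for them the origin only shifts time by a constant. What remains is that the curve is not restricted to responders.

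Part B's primary objective is safety, no hypothesis is tested, and about 13 responders can be reviewed individually from listings. That limits the seriousness of the point. It does not remove it, because a descriptive objective still needs a descriptive output that matches it.

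**Conclusion.** The point holds in limited form. Part B has no composite or responder-restricted measure of durability; only the transfusion component is followed over time. Gradual Hgb loss without transfusion has no patient-level summary, and the pooled observed-case means are a diluted measure of the rest.

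How much this matters depends on how many responders decline slowly without transfusion, which the documents do not say. The 0.10 to 0.50 g/dL range in step 5 rests on assumed mean changes and an assumed four losses. The absence of the output rests on the text alone. This is an inexpensive improvement to the Part B SAP and does not affect the Part A primary analysis.

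**What to change.** Add to Part B SAP section 7, for Part A responders dosed in Part B:

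1. For each 3-month window, the number and proportion (exact 95% CI) with mean on-treatment Hgb in the window at least 12 g/dL or at least 2 g/dL above Part A baseline, and no transfusion or prohibited CAD therapy in that window. Count discontinuation before the sponsor's end of study as not maintained, and tabulate the reasons so that tolerability can be told apart from loss of effect. On-treatment values are needed because the visit 9 weeks after the last dose falls inside the Part B period (5.1.1).
2. Kaplan-Meier time from Week 26 to loss of response, using the same events including discontinuation, censored at the sponsor's end of study. Judge Hgb loss on the same window mean, so that it does not depend on whether Hgb is sampled every 2 or every 4 weeks (Protocol Table 3 footnote t, Table 4 footnote o).
3. By-visit Hgb summaries by Part A response status, with a supportive version setting post-transfusion values to missing as in Part A SAP 5.1.4.

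Keep the current observed-case means as supportive. Hgb, transfusions and prohibited medication are already collected. The cost is SAP wording and two or three tables, wide intervals with about 13 responders, and a durability figure that may look less favourable than the means.
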